7.4.6 Premature Termination (All Cohorts)

If a subject discontinues from the study prior to Week 24, the following assessments should occur prior to oral treprostinil discontinuation or as soon as possible after. The recommended sequence of assessments is as follows:

- PedsQL questionnaire (must be performed as first assessment and as best as possible prior to seeing their physician or healthcare provider or completing any other forms or assessments)
- Pharmacokinetics (Section 3.3.3, if the subject is still receiving oral treprostinil at the time of discontinuation)
- Vital signs (following at least five minutes of rest; collected prior to 6MWT or at least 30 minutes following 6MWT)
- Urine pregnancy test (females of childbearing potential)
- Clinical laboratory parameters
- NT-pro-BNP (prior to 6MWT or CPET)
- Physical examination
- 12-lead ECG (following at least five minutes of rest in the semi-recumbent position)
- PAH symptoms
- Panama and WHO functional classification
- Cardiac MRI (must be performed prior to the 6MWT and CPET if done on the same day; if subject requires anti-anxiety medication (no general anesthesia) during the cMRI (without contrast), then the cMRI should be performed on a separate day from the CPET and 6MWT

- 6MWT/Borg dyspnea score (should occur within 2-6 hours of the subject's last dose of oral treprostinil),includes oximetry and HR recovery monitoring (to be conducted following at least five minutes of rest); Borg dyspnea score to be conducted immediately following 6MWT)
- CPET (should be performed 2-6 hours after the morning dose of oral treprostinil and prior to the next scheduled dose; if performed on same day as 6MWT, CPET should conducted a minimum of two hours after 6MWT)
- Oral treprostinil accountability
- Adverse events
- Concomitant medications

7.4.7 Continued Access Plan

Subjects who have completed the Week 24 Visit will be given the option for continued access to oral treprostinil (Section 3.3.2.7). During the Week 24 Visit, the Investigator should assess each subject's eligibility for the Continued Access Plan.

8 STUDY TERMINATION

8.1 CRITERIA FOR SUBJECT WITHDRAWAL

A subject may voluntarily withdraw or be withdrawn from the study and/or oral treprostinil (study drug) by the Investigator at any time for reasons including, but not limited to, the following:

- Stopping criteria is met
- The subject wishes to withdraw from further participation
- A serious or life-threatening AE occurs or the Investigator considers that it is necessary to discontinue oral treprostinil (study drug) to protect the safety of the subject
- The subject deviated from the protocol
- The subject's behavior is likely to undermine the validity of his/her results
- Subject is female and became pregnant during the course of the study

TDE-PH-206

If a subject is discontinued from the study prematurely, the Investigator must provide an explanation in the eCRF and complete the End of Study Record for that subject. If oral treprostinil (study drug) has been administered, the Investigator should make every effort to perform all scheduled evaluations prior to discharge. In the event that a subject discontinues oral treprostinil prematurely due to an AE, the subject will be followed until either the Investigator determines that the AE has resolved, it is no longer considered clinically significant, the subject is lost to further follow-up, or for 30 days if the adverse event extends beyond the final visit.

8.1.1 Lost to Follow-up

If a subject fails to return to clinic or respond after at least three documented attempts by the site to contact the subject by telephone or email, the Investigator should issue a written letter by certified mail requesting the legal guardian and/or caregiver contact the clinic. If no response is received, the subject will be considered lost to follow-up. The site will record the last date of contact in the eCRF as the termination date.

8.2 CRITERIA FOR TERMINATING THE STUDY

The study may be stopped at any time if, in the opinion of the Investigator and/or Sponsor, continuation of the study represents a serious medical risk to the subjects. This may include, but is not limited to, the presence of serious, life-threatening, or fatal AEs or AEs that are unacceptable in nature, severity, or frequency. The Sponsor reserves the right to discontinue the study for any reason at any time.

8.3 CRITERIA FOR DISCONTINUING THE SITE

The study may also be terminated at a given center if:

- The Principal Investigator elects to discontinue the study
- The Sponsor elects to discontinue the study at the site
- U.S. FDA regulations are not observed
- The protocol is repeatedly violated
- Changes in personnel or facilities adversely affect performance of the study

9 ADVERSE EVENT REPORTING

9.1 **DEFINITIONS**

9.1.1 Adverse Event

An AE is any untoward medical experience occurring to a subject, including any abnormal sign (e.g., abnormal physical exam or laboratory finding), symptom, or disease, temporally associated with the subject's participation in the research, whether or not it is related to the use of the oral treprostinil (study drug).

An AE may include:

- An intercurrent illness, injury, or any other concomitant impairment of the subject's health, as well as abnormal laboratory findings if deemed to have clinical significance.
- A worsening of an existing symptom or condition or post-treatment events that occur as a result of protocol-mandated procedures (e.g., exacerbation of a pre-existing illness following the start of the study or an increase in frequency or intensity of a pre-existing episodic event or condition).

Thus, no causal relationship with the study drug is implied by the use of the term "adverse event".

An AE does not include the following:

- Medical or surgical procedures (e.g., surgery, endoscopy, tooth extraction, transfusion); however, the condition for which the surgery is required may be an adverse event. Planned surgical measures permitted by the study protocol and the condition(s) leading to these measures are not adverse events.
- Day to day fluctuations of pre-existing disease or conditions present or detected at the start of the study that do not worsen.
- Situations where an untoward medical occurrence has not occurred (e.g., hospitalizations for cosmetic elective surgery, social and/or convenience admissions).
- The disease or disorder being studied or a sign or symptom associated with the disease or disorder unless more severe than expected for the subject's condition.

9.1.2 Suspected Adverse Reaction

Suspected adverse reaction means any AE for which there is a reasonable possibility that the oral treprostinil (study drug) caused the AE. For the purposes of safety reporting, 'reasonable possibility' means there is evidence to suggest a causal relationship between the oral treprostinil and the AE, as described in Section 15.4.

9.1.3 Serious Adverse Event

A serious adverse event (SAE) is an AE occurring at any dose that results in any of the following outcomes:

- Death
- A life-threatening AE
- Inpatient hospitalization or prolongation of existing hospitalization
- A persistent or significant disability/incapacity
- A congenital anomaly/birth defect
- Results in a medically important event of reaction

Life-threatening in this context refers to a reaction in which the patient was at risk of death at the time of the reaction; it does not refer to a reaction that hypothetically might have caused death if more severe.

Medical and scientific judgment should be exercised in deciding whether other situations should be considered serious reactions, such as important medical events that might not be immediately life threatening or result in death or hospitalization, but might jeopardize the patient or might require intervention to prevent one of the other outcomes listed above. Examples of such events are intensive treatment in an emergency room or at home for allergic bronchospasm, blood dyscrasias, or convulsions that do not result in hospitalization or development of dependency or abuse. Any suspected transmission via a medicinal product of an infectious agent is also considered a serious adverse reaction.

9.1.4 Adverse Events Anticipated for PAH

Events associated with disease under study:

Expected events that are related to the disease under study are defined in Table 9-1. These events are anticipated to occur in the study population at some frequency independent of drug exposure.

All events that occur during the course of the study that are included on this list and/or felt to be related to the underlying disease under study by the Investigator should NOT be recorded as an AE unless the event is serious or unusual with respect to intensity, frequency, or duration, or there is a reasonable possibility that it may have been caused by oral treprostinil (study drug). These events should be clearly documented in the subject medical record and identified as signs/symptoms of underlying disease under study. All deaths and unplanned hospitalizations, regardless of underlying cause, will be reported as a SAE.
Abdominal pain (Gastrointestinal disorders; ABDOMINAL PAIN)	Hemoptysis (Respiratory, thoracic & mediastinal disorders; HAEMOPTYSIS)
Anorexia (Metabolism and nutrition disorders; DECREASED APPETITE)	Hypoxia (Respiratory, thoracic & mediastinal disorders; HYPOXIA)
Ascites (Gastrointestinal disorders; ASCITES)	Loss of consciousness (Nervous system disorders; LOSS OF CONSCIOUSNESS)
Cardiac arrhythmia (Cardiac disorders; ARRHYTHMIA)	Nausea (Gastrointestinal disorders; NAUSEA)
Cardiac arrest (Cardiac disorders; CARDIAC ARREST)	Edema (General disorders and administration site conditions; OEDEMA)
Heart failure (including exacerbation of) (Cardiac disorders; CARDIAC FAILURE)	Orthopnea (Cardiac disorders; ORTHOPNOEA)
Chest pain (General disorders and administration site conditions; CHEST PAIN)	Pallor (Vascular disorders; PALLOR)
Cardiovascular collapse (Vascular disorders; CIRCULATORY COLLAPSE)	Palpitations (Cardiac disorders; PALPITATIONS)
Cor pulmonale (Cardiac disorders; COR PULMONALE)	Cool extremities (General disorders and administration site conditions; PERIPHERAL COLDNESS)
Cough (Respiratory, thoracic & mediastinal disorders; COUGH)	Pulmonary arterial hypertension, exacerbation of (Vascular disorders; PULMONARY ARTERIAL HYPERTENSION)
Cyanosis (Cardiac disorders; CYANOSIS)	Sudden death (Cardiac disorders; SUDDEN DEATH)
Dizziness (Cardiac disorders; DIZZINESS)	Syncope (Nervous system disorders; SYNCOPE)
Dyspnea at rest (Respiratory, thoracic & mediastinal disorders; DYSPNOEA)	Vasovagal reaction (Nervous system disorders; PRESYNCOPE)
Dyspnea on exertion (Respiratory, thoracic & mediastinal disorders; DYSPNOEA EXERTIONAL)	Tachycardia (Cardiac disorders; TACHYCARDIA)
Paroxysmal nocturnal dyspnea (Cardiac disorders; DYSPNOEA PAROXYSMAL NOCTURNAL)	Vomiting (Gastrointestinal disorders; VOMITING)
Exercise intolerance (General disorders and administration site conditions; EXERCISE TOLERANCE DECREASED)	Weight loss (Investigations; WEIGHT DECREASED)
Fatigue (General disorders and administration site conditions; FATIGUE)	Weight gain (Investigations; WEIGHT INCREASED)

Table 9-1Expected Events Attributable to PAH (System Organ Class and
PREFERRED Term, Ver. 17.1)

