Two 16-week, randomized, double-blind, placebo-controlled, international efficacy and safety studies of oral treprostinil in subjects with WHO Group 1 PAH already receiving treatment with an ERA, PDE-5i or a combination of both have been conducted. The results did not demonstrate a benefit in exercise testing with median 6MWD at Week 16 (11 meters [Hodges-Lehmann estimate; p=0.072] and 10 meters [Hodges-Lehmann estimate; p=0.089], respectively). Subjects were in WHO functional classification II (~23%) and III (~77%) with either idiopathic or heritable PAH (~66%), collagen vascular disease associated PAH (~29%), or PAH associated with HIV (1%) or congenital heart defect (4%). The mean baseline 6MWD was approximately 340 meters. Approximately 40% of enrolled subjects were receiving both an ERA and a PDE-5i.

Over 824 subjects have received oral treprostinil in a long-term, uncontrolled, open-label ongoing extension study. About 70% of subjects continued treatment with oral treprostinil for at least a year. The mean dose was 4.2 mg BID at one year. The dose of oral treprostinil continued to increase over time with doses (mean \pm SD) of 3.6 \pm 2.7, 4.1 \pm 3.1, and 5 \pm 3.7 mg

BID at 6 (n=649), 12 (n=433), and 24 months (n=238), respectively. In the 522 subjects that completed the 12-month efficacy assessment, their mean 6MWD improved by 24 meters compared to baseline (30 meters in subjects not on another PAH therapy and 20 meters when oral treprostinil was used in combination with an ERA and/or a PDE-5i). Of the subjects that remained in the study, overall survival was 92%, 87%, and 82% at the end of 1, 2, and 3-years, respectively, with progression-free survival (progression defined as death, discontinuation or addition of a PAH therapy) of 74%, 61%, and 47%. Reasons for discontinuation from the study included adverse event (16%), progression of disease (15%), death (13%), and withdrawn consent (7%).

The most frequent adverse events (AEs) associated with oral treprostinil that occurred more frequently than placebo in clinical trials were related to systemic effects that are characteristic of prostacyclin (*e.g.*, headache, diarrhea, nausea, flushing, pain in jaw, pain in extremity).

A comprehensive description of oral treprostinil, including the pharmacology, toxicology, and clinical studies completed to date may be found in the Orenitram Package Insert and current version of the Investigators' Brochure.

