#### 11.5 DISEASE-RELATED EVENTS

Disease-related events that appeared or worsened (with clinical significance) during the study will be captured, including abdominal pain, anorexia, ascites, cool extremities, cor pulmonale, cough, cyanosis, hemoptysis, heart failure (or exacerbation of), hypoxia, loss of consciousness, nausea, pallor, palpitations/cardiac arrhythmia, paroxysmal nocturnal dyspnea, exacerbation of pulmonary hypertension, tachycardia, weight loss/gain, vasovagal reaction, and vomiting. The assessment of each of these disease-related events will be listed by cohort and subject. The number and percentage of subjects noting the onset or worsening of each of these events will be summarized by cohort.

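### Nausea is both a named prostacyclin effect and a listed PAH event, the rules for recording it as an AE conflict over new-onset cases, and no planned table combines the two places it is counted

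*Protocol*

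**What the plan says.** Protocol 1.2.4 describes the AEs seen more often on oral treprostinil than on placebo as systemic prostacyclin effects and gives six examples: "headache, diarrhea, nausea, flushing, pain in jaw, pain in extremity".

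Protocol 9.1.4 holds a list of events expected from PAH whatever the drug exposure (Table 9-1). It includes "Nausea (Gastrointestinal disorders; NAUSEA", as well as vomiting, abdominal pain, anorexia, and weight loss and gain. Listed events "should NOT be recorded as an AE unless the event is serious or unusual with respect to intensity, frequency, or duration", with one more exception where the drug may plausibly be the cause. Events left off the AE form go into the medical record. SAP 11.3 restates this rule with the same exceptions.

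Protocol 3.3.2.5 and 9.3 give the rule for the same events with an added exception: an event that is *new* compared with the subject's history is also recorded.

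SAP 11.5 provides a separate capture of disease-related events, limited to clinically significant onset or worsening. It covers nausea, vomiting, abdominal pain, anorexia and weight change. "The number and percentage of subjects noting the onset or worsening of each of these events will be summarized by cohort" (Table 14.3.1.13, Listing 16.2.7.2).

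**The concern.** Safety and tolerability is the primary objective, and Protocol 10.3.3 centres the safety analysis on AE incidence. The study is open label and has no control group, so no comparator can offset a sorting of cases between drug and disease. For ordinary nausea under 9.1.4 and SAP 11.3, the causality judgement decides whether an AE exists at all, when it should only describe an AE already recorded.

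The definitions in Protocol 15.4 do not settle that judgement. A concurrent disease supports a rating of not related, while a plausible biological link to the drug supports a rating of possible. Nausea in a child with PAH who has just started treprostinil can fit either.

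At stake is whether the reported nausea incidence reflects what the children experienced, or partly which protocol section the site read and how its investigator attributes. The consequence goes beyond one count, because the summaries by severity and by drug discontinuation are planned for TEAEs only.

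**Working it through.** The plan states no figure for this rule. The check is therefore a comparison of the texts, followed by an illustration.

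**1. Overlap of the two lists.** Table 9-1 holds 34 terms. Of the six example drug effects in Protocol 1.2.4, one is in Table 9-1: nausea. Vomiting, abdominal pain and anorexia are in Table 9-1, but the documents do not name them as drug effects.

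**2. Routes by which a listed event becomes an AE.**

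| Source | Serious | Unusual | New | Possibly drug-caused |
|---|---|---|---|---|
| Protocol 3.3.2.5 | yes | yes | yes | yes |
| Protocol 9.3 | yes | yes | yes | yes |
| Protocol 9.1.4 | yes | yes | no | yes |
| SAP 11.3 | yes | yes | no | yes |

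Non-serious, not-unusual nausea that first appears after dosing is an AE under the first two rows whatever its cause. Under the last two rows it is an AE only if drug causation is thought possible.

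**3. Where the remainder is counted.** SAP 11.5 covers 22 of the 34 terms, including all the gastrointestinal ones. Of the other 12, 8 fall under the scored PAH symptoms. The last 4 are cardiac arrest, cardiovascular collapse, sudden death and exercise intolerance. Because SAP 11.5 requires clinical significance, a mild case attributed to PAH can miss both tables. The two tables cannot simply be added, since nothing in the documents prevents a subject from appearing in both. The list of tables in SAP 13.1 contains no combined output.

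**4. Illustration.** Let p be the true share of subjects with nausea, a the share of cases attributed to the drug, and u the share of unattributed cases recorded through another exception. All three are assumptions. The share shown in the TEAE table is

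r = p × [1 − (1 − a)(1 − u)].

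The planned Cohort 3 size of 15 is used with p = 40%, which is 6 subjects:

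- a = 50%, u = 0: 0.40 × [1 − 0.5 × 1] = 0.20, or 3/15.
- a = 50%, u = 50%: 0.40 × [1 − 0.5 × 0.5] = 0.30, an expected 4.5 of 15.
- a = 80%, u = 0 to 50%: 0.32 to 0.36, an expected 4.8 to 5.4 of 15.
- a = 100%, any u: 0.40, no loss.
- All cases new and the *new* exception applied (u = 100%): 0.40, or 6/15, no loss.

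With p = 60% (9 subjects) and a = 50%, the table shows 30% to 45% as u goes from 0 to 50%. Under-counting occurs whenever a and u are both below 100%.

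**The case against.** The case on the other side has several parts.

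- **Other routes exist.** A reader might infer that the TEAE tables will hold only cases the investigator blames on the drug. The documents do not support that. Serious and unusual cases are recorded whatever the attribution, and under 3.3.2.5 and 9.3 so are new ones.
- **The bar for attribution is low.** Under Protocol 15.4, reasonable timing or a plausible biological link can each support a rating of possible, and nausea after starting this drug would often qualify. This makes a large loss less likely. It does not remove the discretion, because an alternative explanation judged likely supports the opposite rating.
- **There is no clear contradiction with the AE definition.** A reader might set 9.1.4 against 9.1.1, which counts untoward experiences "whether or not it is related to the use of the oral treprostinil (study drug". But 9.1.1 itself leaves out symptoms of the studied disease unless they are worse than expected. Section 9.1.4 applies that exclusion. The conflict that stands is the one over *new* events.
- **Only nausea is a named drug effect.** It is tempting to extend the point to entries such as "Vomiting (Gastrointestinal disorders; VOMITING", "Abdominal pain (Gastrointestinal disorders; ABDOMINAL PAIN" or "Anorexia (Metabolism and nutrition disorders; DECREASED APPETITE" as effects the sponsor expects of the drug. The six effects in 1.2.4 are examples, but the documents name none of these three, so a change to the recording rule has to rest on nausea.
- **Excluded cases are not necessarily lost.** SAP 11.5 tabulates clinically significant cases by cohort with no attribution condition, and both data sources are listed by subject. Cohort 1 also completes a daily prostacyclin-related AE diary in hospital. These are real mitigations, but partial ones: the diary does not cover Cohorts 2 and 3, SAP 13 names no output for it, and a reader would have to build the combined count from two listings.

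**Conclusion.** The point holds in a limited form. Under Protocol 9.1.4 and SAP 11.3, nausea that is neither serious nor unusual enters the TEAE tables only by open-label attribution. Under Protocol 3.3.2.5 and 9.3, new-onset nausea is recorded regardless. These passages must be reconciled, because the reported incidence of a known drug effect otherwise depends on site practice. The separate disease-related event table reduces the problem without resolving it.

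The size cannot be known from the documents. The illustration runs from no loss (40% shown as 40%) to half the cases missing (40% shown as 20%). It rests on assumed values for the true incidence, the attribution share and the use of the other exceptions. The conclusion that under-counting is possible needs only that some unattributed cases meet no exception at the site concerned. The correction is a cheap improvement to a primary tolerability outcome. The point does not show that the safety data are unusable.

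**What to change.** 1. **Reconcile the recording rule** across Protocol 3.3.2.5, 9.1.4 and 9.3 and SAP 11.3. Listed events with new onset after the first dose should be recorded as AEs with causality rated separately, at least for nausea.
2. **Add one table to SAP 11.3/11.5.** For each cohort and each term found in both sources, give the number and percentage of subjects with the event after first dose in either the AE data or the disease-related event data. Count each subject once, regardless of attribution. Listings 16.2.7.1 and 16.2.7.2 already hold both sources by subject. SAP 8 puts the assessment date and study day on listings, which should allow the restriction to the period after first dose.

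The cost is one wording change, one derived table and probably a less favourable reported incidence. If the rule changes mid-study, AE collection will differ between earlier and later subjects. The combined table mitigates that, although it cannot recover mild cases that entered neither source. If data collection has finished, only the second step remains available, and the study report should state which recording rule the sites applied.
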